#### **9.2.1 Inclusion criteria**

1. Subjects who have consented to Section 3 of the document: "GDPR – what this means to you" (Appendix A) as part of a clinical routine visit.
2. Fitted unilaterally or bilaterally with the Ponto 3 SuperPower(s) on abutment(s)
3. Adult subjects (18 years or older)
4. Patient has attended a clinical routine visit where fitting of Ponto 3 SuperPower has been performed and at least one following clinical routine visit where audiological measurements has been performed

#### **9.2.2 Exclusion criteria**

There are no exclusion criteria in this study due to the retrospective nature of the study.

#### **9.2.3 Procedure for identifying potential candidates**

Potential candidates will be identified via the Investigators knowledge of the clinic's pool of patients with Ponto 3 SuperPower.

The medical records, Genie Medical and Auditbase at Norfolk and Norwich university hospital will be basis for identifying relevant data during the period of data collection in order to collect described data, by investigator, starting from the date 01-01-2017.

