### 9.1.1 Subject enrolment

The investigational device Ponto 3 SuperPower used in the study is CE marked and FDA cleared and has been commercially available since December 2016, which is approximately 4 years. To have a wide representative selection of subjects, enrollment will be spread over the 4 years, ensuring capture of the population fitted with Ponto 3 SuperPower at the clinic over the time when the device has been available.

In this retrospective study 55 patients will be included in the study. The total number of test subjects will include the aim of having around 15 with hearing loss <45 dB HL, around 15 with mixed hearing loss 45>≤55 dB HL and around 15 with a mixed hearing loss >55 dB HL, this to represent all indications for Ponto 3 SuperPower and a wide spread in hearing loss degree.

The data will be collected from the subjects in the time period from the clinical routine visit where the Ponto 3 SuperPower where fitted or just prior, and from the clinical routine visit following the fitting, where audiologic fitting follow-up procedures are performed (approximately 3 months).

 The data from this column can be spread across the first 2 follow-up clinical routine visits following the fitting visit

 Masked and unmasked, might have been performed prior to the clinical routine visit where Ponto 3 SuperPower was fitted

 Aided for CHL/MHL patients, and unaided and aided in the implanted or non-implanted side for SSD patients.

 Might have been performed at the clinical routine visit where Ponto 3 SuperPower was fitted or at the clinical routine visit following the fitting.

The collection of the patient's data will be performed like this: The subjects are included over the last 4 years where the Ponto 3 SuperPower has been on the market, the aim is to distribute the subjects as equal as possible over the years 2017 to 2020. As the COVID-19 pandemic had an impact on the hospitals ability to see patients for clinical routine rehabilitation visit, fewer patients have been fitted with Ponto 3 SuperPower during 2020. Thus, a lower number of subjects will be included from 2020 is expected. Dependent on the enrollment of subject from 2020, approximately 20 subjects are collected from each year from 2017-2019.

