#### 9.3.3.4 Functional gain

The functional gain is a calculation and uses the masked, if not available unmasked, AC thresholds obtained with headphone TDH39 and aided sound field thresholds as described above (9.3.3.1-9.3.3.3). Functional gain is defined as the difference between the unaided AC and aided sound field thresholds. Functional gain can be calculated for frequencies 500Hz, 1kHz, 2 kHz, 3kHz and 4kHz. The average functional gain will be also be calculated for PTA4.

No blocking or masking of the non-implanted ear has been performed during the sound field measurement.

Unaided AC for the implanted ear will be used for the calculation of functional gain. In case of a bilateral Ponto fitting it is the best ear AC that will be used.

The aided soundfield has only been conducted on patients with CHL/MHL, and not for SSD.

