**Table 8. Overview of retrospective studies including functional gain as outcome measure.**

Due to the retrospective design, no drop-outs are considered. Based on the typical sample size in similar studies within state-of-the-art and achieving a sufficient number of patient represented in the hearing loss categories for CHL/MHL population (see section 9.1.1), 55 subjects was concluded as an appropriate number to include in the study.

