## 14 DEVIATIONS FROM CLINICAL INVESTIGATION PLAN

A CIP deviation is an intentional or unintentional failure to follow the requirements of the CIP. Every effort should be made to comply with the requirements of the CIP. The Investigator, and other representatives of the investigational site team, is not allowed to deviate from the CIP, unless needed to protect the rights, safety and well-being of the subjects (i.e. emergencies). However, as there will be no study visits, and all

data collected for this study are already existing in the patients' medical files, no major deviations are expected. The sponsor is aware that there might be some datapoints missing in the final datafile, due to the fact that they might not have been collected originally. These will not be regarded as deviations

If other deviations occur, the Investigator should inform the monitor/clinical trial manager and make a record in the CIP Deviation Log provided in the study site file. The implications of the deviation must be reviewed and discussed between the Sponsor and the Investigator. If deviations are found during monitoring visits, they should also be documented in the monitoring report and handled as above. This should be done as soon as possible after detection to avoid repetitive deviations. Continuous review of protocol deviations during monitoring visits aim to detect systematic errors and to identify retraining needs at the site. Frequency of monitoring is described in the monitoring plan and should be increased if systematic deviations are identified. All protocol deviations must be documented stating the reason, date, the action(s) taken, and the impact for the subjects and/or the study. If serious or repeated deviations occur at a site, the Sponsor has the right to initiate early termination of the study.

At the end of the study, or in connection to a predefined interim analysis, protocol deviations, if any, will be categorized as minor or major and their consequence on analysis populations will be determined.

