## 17 INFORMED CONSENT PROCEDURE

No study specific informed consent will be collected from the patients. As this is an observational (non-interventional) retrospective investigation the informed consent usually required for human research subjects may be waived by an ethics committee.

The rational for arguing for a waiver from the investigation-related informed consent requirement is mainly related to the nature and type of investigation, as indicated above. There are also additional arguments which may be considered for this investigation; the additional workload (disproportionate effort) for the investigation site team and the potential bias in subject inclusion (e.g. patients that either doesn't respond

to the invitation or refuse participation) with corresponding scientific shortcomings. To ensure high quality data, partly by including as many applicable subjects into the investigation as possible, there is a need to enhance subject recruitment without the corresponding disproportionate effort and population bias an informed consent procedure would impose. Should an informed consent be required for this retrospective non-interventional investigation there is a potential risk for non-responsiveness and refusals that may result in inconclusive and biased data on e.g. non-users, indications, types of hearing losses etc.

In an effort to comply with applicable subject data protection regulations while developing service improvements all patients treated at the investigation site, as part of the daily clinical routine practice, are asked to provide their consent to the document: "GDPR – what this means to you" (Appendix A). Section 3 of this document reads:

*"We may also share information about you which will not identify you as an individual for our Service Improvement such as patient experience, patient survey or improvement regarding your treatment if you have had any. Again, you may decide you do not want us to use your information for research and trials, but it will help the hospital"*

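### Protocol 9.2.3 finds candidates through the investigator's knowledge of the clinic; a records-based list with a fixed inclusion rule would be a cheap improvement

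*Protocol*

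**What the plan says.** Protocol 9.2.3 gives one route to candidates: "Potential candidates will be identified via the Investigators knowledge of the clinic's pool of patients with Ponto 3 SuperPower". Its next sentence names the medical records, Genie Medical and Auditbase, but as the place to find the data, not as a frame from which patients are listed. In 9.1.2 the investigator checks the patient against the medical file. There are four inclusion criteria (9.2.1) and no exclusions (9.2.2).

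Section 9.1.1 states the aims. Enrolment is spread over four years so as to be representative, "ensuring capture of the population fitted with Ponto 3 SuperPower at the clinic over the time when the device has been available". The total is 55. By year, and depending on how many come from 2020, "approximately 20 subjects are collected from each year from 2017-2019". By severity, "The total number of test subjects will include the aim of having around 15 with hearing loss" below 45 dB HL, with around 15 in each of two higher bands. Section 17, arguing for the consent waiver, speaks of high-quality data obtained "partly by including as many applicable subjects into the investigation as possible".

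Section 14 notes that all "data collected for this study are already existing in the" patients' medical files. Section 17 adds that the investigators who collect the data also work in the clinic's daily routine. In the SAP, the ITT population is everyone included (2.1), disposition is counted from those included (4.3), and the main outcome is the mean functional gain with its 95% CI (4.6.1).

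**The concern.** In a single-arm retrospective study the mean describes the fitted population only as well as the included patients represent it. Here the outcome exists before the patient is chosen, and those who choose may already know how the patient did. The plan neither prevents that knowledge from influencing the choice nor visibly provides for counting the eligible patients left out. A confidence interval reflects sampling variation only, so it would not show a shift caused by selection.

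What is at stake is representativeness, which the protocol itself sets as an aim in 9.1.1 and relies on in section 17, where it argues that a consent procedure would bias inclusion. No decision threshold is at risk: Protocol 11.2 states no hypothesis for the primary endpoint and 11.3 applies no pass/fail criteria.

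**Working it through.** **Can the plan's own figure be reproduced?** The total of 55 rests on the size of earlier retrospective studies and on "achieving a sufficient number of patient represented in the hearing loss categories for CHL/MHL population" (Protocol 11.2). It has no power formula, so there is nothing to recompute. The targets can be added up:

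- Bands: 3 × 15 = 45, leaving 55 − 45 = 10 unallocated.
- Years: 3 × 20 = 60 for 2017-2019, which is 5 above 55 before any 2020 patient. The source makes this figure approximate and conditional on 2020; 3 × 18 = 54 would fit.

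Neither set says which patient fills a place.

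**How large could the effect be?** This is an illustration only. The documents give no pool size, no SD and no link between inclusion and outcome, so all three are assumed.

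- Number analysed: functional gain exists only for CHL/MHL (Protocol 9.3.3.4: "The aided soundfield has only been conducted on patients with CHL/MHL, and not for SSD"). The band targets suggest n = 45.
- 95% CI half-width in SD units = t(0.975, n−1)/√n. At n = 45 this is 0.300. If measurements are missing it is 0.320 at n = 40 and 0.343 at n = 35.
- Shift of the mean in SD units = ρ × √((1−f)/f). Here f = 45/N, N is the number of eligible CHL/MHL patients, and ρ is the correlation between being included (0/1) and functional gain. The assumed range is 0.1 to 0.3, in either direction.
- Gap between the means of those taken and not taken, implied by ρ, in SD units = ρ/√(f(1−f)).

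| N eligible | f | √((1−f)/f) | Shift, ρ = 0.1 to 0.3 | Shift ÷ 0.300 | Gap at ρ = 0.3 |
|---|---|---|---|---|---|
| 45 | 1.00 | 0 | 0 | 0 | none left out |
| 50 | 0.90 | 0.333 | 0.03 to 0.10 SD | 0.11 to 0.33 | 1.00 SD |
| 60 | 0.75 | 0.577 | 0.06 to 0.17 SD | 0.19 to 0.58 | 0.69 SD |
| 90 | 0.50 | 1.000 | 0.10 to 0.30 SD | 0.33 to 1.00 | 0.60 SD |

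The last column shows what the upper values require. A shift of a full half-width needs half the eligible CHL/MHL patients left out and a 0.60 SD difference between the halves. If ρ is read instead as a correlation with a latent normal selection score, the factor at f = 0.5 is 0.798. The shift is then 0.08 to 0.24 SD, at most 0.80 of the half-width. The year and band targets are not modelled.

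**Under the proposed rule.** If all eligible patients are taken, f = 1 and the shift within the eligible pool is 0. A random sample has expected ρ = 0. A consecutive sample removes the investigator's choice.

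**The case against.** The strongest reply is that this is one clinic whose investigators see these patients routinely, so knowledge of the pool may simply mean the whole pool. The stated purpose in 9.1.1, the file check in 9.1.2 and the intent in section 17 all point that way. If about 55 patients are eligible, the point has almost no practical effect. This stands as a limit on the size of the concern. It does not supply a rule: section 17 gives a reason for a waiver, and 9.1.2 applies to the criteria, not to how candidates are found.

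Second, relevant text may be out of sight. Part of Protocol 6.1 is blacked out and could contain the pool size. A sentence in 9.1 is also cut, but parallel sentences in Protocol 9.2 and SAP 1.2 suggest that it adds only the market date. The detail of the disposition table sits in a separate guideline (SAP 7), so its title does not settle whether patients left out are counted. These points stand; the claim is confined to the readable text. The Subject Identification Log in section 12 covers included subjects only.

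Third, a reader might infer that favourable patients were picked, or that the 60 against 55 shows a surplus of candidates. The documents support neither. They describe no selection that took place, and the year figure is conditional and approximate, so it may be loose drafting.

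**Conclusion.** The point holds as a cheap improvement. The procedure is underspecified, not shown to be selective. It does not secure the representativeness that Protocol 9.1.1 aims for, and it leaves a possible shift in the mean that the 95% CI would not reflect. The direction is unknown. On the assumed inputs the size runs from nil, when everyone eligible is taken, to about one CI half-width (0.30 SD), when half are left out and the two halves differ by 0.60 SD. At ρ = 0.1 it is at most a third of a half-width. It would be wrong to read this as a finding that the reported mean is biased, or as a defect that invalidates a descriptive study.

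**What to change.** Replace the first sentence of Protocol 9.2.3 with wording such as: 'All adults fitted with Ponto 3 SuperPower on abutment in the study period will be listed from the medical records, Genie Medical and Auditbase, and criteria 1-4 applied to each. All who qualify will be included; if more than 55 qualify, a consecutive or computer-random sample will be taken within fitting year, with the order fixed before outcomes are extracted.'

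Treat the hearing-loss bands as descriptive aims, not as sampling cells. Crossing four years with three bands plus SSD would give up to 4 × 4 = 16 cells for 55 patients, about 3.4 each, which is more than is needed. Under SAP 4.3, report the numbers listed, eligible, included and not included, using counts only for patients without the criterion 1 consent. In the same edit, settle one start date (9.2.3 has 01-01-2017, 11.1 has December 2016) and reconcile the year targets with the total of 55.

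The cost is clerical time for the listing (more if the systems cannot search by device and fitting date, which the documents do not say), band targets met less exactly, and a check under Protocol 13 on whether the amendment needs ethics committee approval. No new patients or procedures are needed. Selection through prior consent, follow-up attendance and missing measurements remains.

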#### **9.2.4 Subject withdrawal**

Not applicable as the study is retrospective study.

### **9.3 Clinical Investigation Procedures**

#### **9.3.1 Subject characteristics**

	Title Investigating hearing with Ponto 3 SuperPower, a bone anchored hearing aid	Document no Doc-00072164	Revision 3	Page 13(29)
---	--	------------------------------------	----------------------	-----------------------

The following subject characteristics will be collected:

- Gender
- Age at fitting visit
- Type of hearing/hearing loss on right and left ear (MHL/CHL; SSD and SNHL, normal hearing)
- Type of hearing solution on right and/or left ear
- BAHS surgery, side(s) and year
- Date of Ponto 3 SuperPower fitting on abutment (mm.year)
- Connectivity devices (device: Oticon Medical streamer, ConnectLine Tv adapter, ConnectLine microphone, Connectline phone adapter, usage: )

### 9.3.2 Safety assessments

This study is a retrospective study, only focusing on the performance of the Ponto 3 Superpower, and only collecting data during the short interval between the clinical routine visit where the Ponto 3 SuperPower has been fitted or just prior to that visit (where audiology thresholds might have been performed, see 9.3.3.1) and the subsequent clinical routine visit(s) following the fitting, therefore there are no safety risk involved. Safety events, see section 18, will be collected to the following extent; if the investigator finds documentation in the audiological file regarding mentioning of a safety event, these will be recorded in the e-CRF. Only the audiology file will be reviewed and only for the time of the data collection time window. Any adverse event (AE) that is judged as related to the device by the investigator will be reconciled against the Sponsor's complaint system, and if not previously reported added as a new complaint. Any device-related AE will be investigated according to the Sponsor's procedure for complaint handling.

### 9.3.3 Data Collection

Any information on how the data obtained in this retrospective study have been described to reflect the Norwich and Norfolk university hospital's routine.

#### 9.3.3.1 Collection of Pure tone thresholds from audiogram measured prior to fitting of Ponto 3 SuperPower

Unmasked and if available masked BC thresholds for frequencies 500 Hz, 1kHz and 2 kHz and AC thresholds for frequencies 250 Hz, 500Hz, 1kHz, 2 kHz, 3kHz, 4kHz, 6kHz and 8kHz will be collected from audiogram obtained prior to Ponto 3 SuperPower were fitted.

#### 9.3.3.2 Collection of BC In-situ thresholds from BC In-situ audiogram measured during fitting of Ponto 3 SuperPower

BC In-situ thresholds for frequencies 250 Hz, 500 Hz, 1 kHz, 2 kHz, 3 kHz, 4 kHz, 6 kHz and 8 kHz will be collected from the BC In-situ audiogram obtained when Ponto 3 SuperPower were fitted.

#### 9.3.3.3 Collection of Aided sound field thresholds measured with the Ponto 3 SuperPower

Sound field thresholds for frequencies 500Hz, 1kHz, 2 kHz, 3kHz and 4kHz will be collected from sound field audiogram obtained as follow-up after Ponto 3 SuperPower fitting, typically this is collected 3 months post fitting, alternatively from the fitting visit. Thresholds will be obtained aided for the CHL/MHL patients.

Sound field thresholds are obtained 1-2 m azimuth. The measurement has been conducted with the contralateral ear left open, hence no masking has been applied. The measurement has been conducted in the patients user settings, with no disabling of DFC or NR. The directionality has been in user settings, which for most patients is an [automatic TriMode] which during this measurement was equivalent to have the device in an omni mode, because the measurement is conducted in a quiet room with warble tones

from the front.

#### 9.3.3.4 Functional gain

The functional gain is a calculation and uses the masked, if not available unmasked, AC thresholds obtained with headphone TDH39 and aided sound field thresholds as described above (9.3.3.1-9.3.3.3). Functional gain is defined as the difference between the unaided AC and aided sound field thresholds. Functional gain can be calculated for frequencies 500Hz, 1kHz, 2 kHz, 3kHz and 4kHz. The average functional gain will be also be calculated for PTA4.

No blocking or masking of the non-implanted ear has been performed during the sound field measurement.

Unaided AC for the implanted ear will be used for the calculation of functional gain. In case of a bilateral Ponto fitting it is the best ear AC that will be used.

The aided soundfield has only been conducted on patients with CHL/MHL, and not for SSD.

#### 9.3.3.5 Effective gain

Effective gain is a calculation and is defined as the difference between aided sound field thresholds measurement with Ponto 3 SuperPower(s) and BC In-situ thresholds at the time when the Ponto 3 SuperPower was fitted as described above (9.3.3.3-9.3.3.2). Effective gain can be calculated for frequencies 250 Hz, 500Hz, 1 kHz, 2 kHz, 3 kHz and 4 kHz. The average effective gain will be calculated for PTA4.

#### 9.3.3.6 Collection of speech intelligibility scores

Speech intelligibility is measured in a sound treated room using sentence tests. The sentence tests used at Norwich and Norfolk hospital is the The AB[s] Isophonemic Monosyllabic Word test (7) and/or the BKB (Bamford-Kowal-Bench). BKB is never measured with SSD patients.

The sentence tests are measured in quiet and/or with background speech-weighted noise.

For patients with CHL/MHL speech intelligibility (percent (%)) was collected in quiet at the level of 60-65 dB HL for aided condition. For speech in noise the speech intelligibility percent (%) will be collected at the speech level of 60-65 dB HL when speech is presented from the front (0°) and 50-55 dB HL noise is presented from behind (180°) for aided condition.

For patients with SSD speech intelligibility in noise (percent (%)) was collected for unaided and aided conditions for two test setups with +10 dB fixed signal to noise ratio (SNR) : 1. Speech signal at 60-65 dB HL directed to the implanted ear and noise at 50-55 dB HL directed to the non-implanted ear, and 2. Speech signal at 60-65 dB HL directed to the non-implanted ear and noise at 50 -55 dB HL directed to the implanted ear.

All measurements have been conducted in user settings, and with no masking or plugging of the contralateral ear in case of unilateral patient.

Population	Speech test in quiet (%) – BKB 	Speech test in quiet (%) – AB[s]	Speech test in noise (%) at fixed SNR (+10 dB) – BKB 	Speech test in noise (%) at fixed SNR (+10 dB) – AB[s]	Loudspeakers
CHL/MHL	60-65 dB HL	60-65 dB HL	Speech 60-65 dB HL Noise 50-55 dB HL	Speech 60-65 dB HL Noise 50-55 dB HL	Speech (0°) Noise (180°)
SSD				Speech 60-65 dB HL Noise 50-55 dB HL	Simulated non-implanted

Population	Speech test in quiet (%) – BKB 	Speech test in quiet (%) – AB[s]	Speech test in noise (%) at fixed SNR (+10 dB) – BKB 	Speech test in noise (%) at fixed SNR (+10 dB) – AB[s]	Loudspeakers
SSD				Speech 60-65 dB HL Noise 50-55 dB HL	S non-implanted N implanted

 Only conducted as per the audiologist discretion.

